#### Primary estimand 2:

- 1. Population: the same as primary estimand 1
- 2. Variable: Patient-level positive predictive value (PPV), defined as the proportion of participants who have at least one true positive lesion (anatomically localized correspondence between [18F]CTT1057 PET imaging and the reference standard), regardless of any co-existent false positive findings, out of all PET positive participants, using central reads.
- 3. Treatment of interest: the same as primary estimand 1
- 4. Intercurrent events: the same as primary estimand 1
- 5. Summary measure: Patient-level PPV along with two-sided exact binomial 95% confidence interval.

#### 2 Statistical methods

## 2.1 Data analysis general information

The final analysis will be performed by Novartis. SAS version 9.4 or later will be used to perform all data analyses and to generate tables, figures and listings.

#### Data included in the analysis

Only one final analysis is planned for the co-primary efficacy endpoints. All statistical analyses will be performed using all data collected in the database up to the data cut-off date. The cut-off date for the final analysis of study data will be established after all randomized participants have completed EOS visit (Last Patient Last Visit).

All events with start date before or on the cut-off date and end date after the cut-off date will be reported as 'ongoing'. The same rule will be applied to events starting before or on cut-off date and not having documented end date. This approach applies, in particular, to adverse event and concomitant medication reports. For these cases, the end date will not be imputed and therefore will not appear in the listings.

#### **General analysis conventions**

**Pooling of centers:** Unless specified otherwise, data from all study centers will be pooled for the analysis. No center effect will be assessed.

**Qualitative data** (e.g., race, etc.) will be summarized by tables; a missing category will be included as applicable. Percentages will be calculated using the number of participants in the relevant population or subgroup as the denominator.

**Quantitative data** (e.g., age, body weight, etc.) will be summarized by appropriate descriptive statistics (i.e. mean, standard deviation, median, 1st and 3rd quartiles, minimum, and maximum).

#### 2.1.1 General definitions

**Investigational PET imaging agents:** [18F]CTT1057

**Study Treatment:** the administration of at least one of the two PET imaging agents: [F]CTT1057, as a single injection intravenously (i.v.) of approximately 370 MBq (range 266 – 407 MBq), and [Ga]Ga-PSMA-11 as a single injection intravenously (i.v.) of approximately 150 MBq (range 111 – 185 MBq), independently of whether the PET/CT scans were acquired or not. In this study, the investigational imaging agent of interest is the radioligand imaging compound [F]CTT1057. [Ga]Ga-PSMA-11 will be used as a component of the CTS Level 2 if required, and in all participants for the secondary endpoint of assessment of concordance between [F]CTT1057 and [Ga]Ga-PSMA-11 for detection of lesions (as detailed in the study protocol Section 2).

#### Date of administration of investigational PET imaging agents

The date of administration of investigational PET imaging agent is defined as the date when a non-zero dose of investigational PET imaging agent is administered and recorded on the study treatment (e)CRF. The date of administration of study treatment will also be referred as start of investigational PET imaging agent.

#### Study day

The study day describes the day of the event or assessment date, relative to the reference start date.

The study day is defined as:

- The date of the event (visit date, onset date of an event, assessment date etc.) reference start date + 1 if event is on or after the reference start date;
- The date of the event (visit date, onset date of an event, assessment date etc.) reference start date if event precedes the reference start date.

The reference date for all assessments (safety, efficacy, etc) is the start of study treatment.

The study day will be displayed in the data listings. If an event starts before the reference start date, the study day displayed on the listing will be negative.

#### Time unit

A year length is defined as 365.25 days. A month length is 30.4375 days (365.25/12). If duration is reported in months, duration in days will be divided by 30.4375. If duration is reported in years, duration in days will be divided by 365.25.

#### **Baseline**

For safety evaluations, the last available assessment on or before the date/time of start of study treatment [18F]CTT1057 is defined as "baseline" assessment for [18F]CTT1057 safety.

The last available assessment on or before the date/time of start of study treatment [Ga]Ga-PSMA-11 is defined as "baseline" assessment for [Ga]Ga-PSMA-11 safety.

If participants have no value as defined above, the baseline result will be set to missing.

Efficacy evaluations will not include any comparisons between baseline and post-baseline values, and therefore a baseline definition for efficacy evaluations does not apply.

#### On-treatment assessment/event and observation periods

For adverse event reporting, the overall observation period will be divided into three mutually exclusive segments:

- 1. *pre-treatment period*: from day of participant's informed consent to the day/time before administration of study treatment
- 2. *on-treatment period*: from date of first administration of study treatment to 14 days after date of actual administration of any study treatment (including the administration date). The on–treatment period will be divided into the F-on-treatment period and Ga-on-treatment period for the respective study treatment of [18F]CTT1057 or [68Ga]Ga-PSMA-11
  - The F-on-treatment period is from the date of [F]CTT1057 administration to 14 days after the date of [F]CTT1057 administration.
  - The Ga-on-treatment period is from the date of [Ga]Ga-PSMA-11 administration to 14 days after the date of [Ga]Ga-PSMA-11 administration.
- 3. *post-treatment period*: starting 15 days after the date of last administration of study treatment.

Safety summaries (tables, figures) include only data from the on-treatment period with the exception of baseline data which will also be summarized where appropriate (e.g. change from baseline summaries). In addition, a separate summary for death including on-treatment and

post-treatment deaths will be provided. In particular, summary tables for adverse events (AEs) will summarize *treatment-emergent* AEs only (see Section 2.7.1).

However, all safety data (including those from the post-treatment period) will be listed and those collected during the pre-treatment and post-treatment period will be flagged.

#### Windows for multiple assessments

In order to summarize weight, vital signs, and laboratory tests collected over time (including unscheduled visits), the assessments will be time slotted. The following general rule will be applied in creating the assessment windows: If more than one assessment is done within the same time window, the assessment performed closest to the target date will be used. If 2 assessments within a time window are equidistant from the target date, then the earlier of the 2 assessments will be used. If there are multiple assessments on the same date then the worst case value will be used. Data from all assessments (scheduled and unscheduled), including multiple assessments, will be listed.

For participants randomized into sequence 1: [18F]CTT1057 - [68Ga]Ga-PSMA-11

Time Window	Planned Visit Timing	Time Window Definition
On treatment		
Baseline for [18F]CTT1057	On or before Study Day 1*	≤ Study Day 1, and time prior to [  F]CTT1057 injection
Day 1 for [18F]CTT1057	Study Day 1	Date of [18F]CTT1057 injection
Day 15 for PET for [18F]CTT1057	Study Day 15	Study Day 15 - 22, and time prior to [  Ga]Ga-PSMA-11 injection
Baseline (Day 1) for [68Ga]Ga-PSMA-11	On or before [  Ga]Ga-PSMA-11 injection and after [  F]CTT1057 injection	≥Study Day 15 and ≤ Study Day 22, time prior to [  Ga]Ga-PSMA-11 injection
Day 1 for [  Ga]Ga- PSMA-11	On [  Ga]Ga-PSMA-11 injection	Date of [  Ga]Ga-PSMA-11 injection

\*Study Day 1 = the date of [18F]CTT1057 injection

For participants randomized into sequence 2: [68Ga]Ga-PSMA-11 - [18F]CTT1057

Time Window	Planned Visit Timing	Time Window Definition	
On treatment			
Baseline for [  Ga]Ga- PSMA-11	On or before Study Day 1*	≤ Study Day 1, and time prior to [  Ga]Ga-PSMA-11 injection	
Day 1 for [  Ga]Ga- PSMA-11	Study Day 1	Date of [  Ga]Ga-PSMA- 11injection	
Day 15 for PET for [  Ga]Ga-PSMA-11	Study Day 15	Study Day 15 - 22, time prior to [  F]CTT1057 injection	
Baseline for [18F]CTT1057	On or before [  F]CTT1057 and after [  Ga]Ga-PSMA-11	≥Study Day 15 and ≤ Study Day 22, time prior to [18F]CTT1057 injection	
Day 1 for [18F]CTT1057	On [18F]CTT1057 injection	Date of [  F]CTT1057 injection	
Day 15 for [18F]CTT1057	the date of [18F]CTT1057 injection + 14 days	Study Day 29-39	

\*Study Day 1 = the date of [68Ga]Ga-PSMA-11 injection

For vital signs, post-injection/pre-imaging, and post-imaging assessment will be compared to the baseline (pre-injection assessment) in addition to its Day 15 assessment compared to baseline. Post-injection/pre-imaging and post-imaging will be performed on the day of imaging.

#### 2.2 Analysis sets

The Full Analysis Set (FAS) includes all randomized participants.

The Efficacy Analysis Set (EFF) includes all randomized participants who receive the dose of investigational treatment (i.e. [18F]CTT1057), have both an evaluable [18F]CTT1057 PET/CT scan imaging and at least one evaluable CTS assessment, and have not received any prohibited systemic antineoplastic therapy before the completion of PET/CTs and CTS procedures.

The [18F]CTT1057 Safety Set (F-SAF) includes all participants who received the investigational treatment (i.e. [18F]CTT1057).

The [68Ga]Ga-PSMA-11 Safety Set (Ga-SAF) includes all participants who received [68Ga]Ga-PSMA-11. Participants will be analyzed according to the study treatment received.

The **Safety Set (SAF)** includes all participants who received at least one of [F]CTT1057 or [Ga]Ga-PSMA-11.

The number (%) of participants in each analysis set will be summarized and information about analysis sets for each participant will be displayed in a listing.

#### 2.2.1 Subgroup of interest

The primary and secondary efficacy endpoints will be summarized by initial definitive therapy received:

- prior radical prostatectomy
- prior curative intent radiation therapy

The primary efficacy co-primary endpoints will also be summarized by PSA level at baseline (from central laboratory):

- $PSA \le 0.5 \text{ ng/mL}$
- $0.5 \text{ ng/mL} < PSA \le 1 \text{ ng/mL}$
- 1 ng/mL<PSA\leq 2 ng/mL
- $2 \text{ ng/mL} < PSA \le 5 \text{ ng/mL}$
- PSA > 5 ng/mL

# 2.3 Patient disposition, demographics and other baseline characteristics

#### 2.3.1 Patient disposition

Enrollment by country or subdivision and center will be summarized for all screened participants. The number (%) of screen failure and the reasons for screening failure will be displayed. For participants screened more than once, the data from the last screening visit will be used in the summaries. The following summaries will be provided (with % based on the total number of FAS participants unless otherwise specified):

- Number (%) of participants who were screened (based on the 'Disposition' page and with % based on all screened participants)
- Number (%) of participants who completed the screening phase and were randomized (based on the 'Disposition' page and with % based on all screened participants)

- Number (%) of participants who did not complete screening (were not randomized) with reason (based on the 'Disposition' page and with % based on all screened participants)
  - Number (%) of participants who did not complete screening related to COVID-19 and primary relationships to COVID-19 (based on the 'Disposition' page and with % based on all screened participants)

The following summaries will be displayed by assigned treatment sequence and overall:

- Number (%) of participants who completed treatment period 1 (based on the 'Disposition' page)
- Number (%) of participants who discontinued treatment period 1 with reason (based on the 'Disposition' page)
  - Number (%) of participants who discontinued treatment period 1 related to COVID-19 and primary relationships to COVID-19 (based on the 'Disposition' page)
- Number (%) of participants who completed treatment period 2 (based on the 'Disposition' page)
- Number (%) of participants who discontinued treatment period 2 with reason (based on the 'Disposition' page)
  - Number (%) of participants who discontinued treatment period 2 related to COVID-19 and primary relationships to COVID-19 (based on the 'Disposition' page)
- Number (%) of participants who completed the study (based on the 'Disposition' page)
- Number (%) of participants who discontinued the study and the reason for discontinuation (based on the 'Disposition' page)
  - Number (%) of participants who discontinued the study related to COVID-19 and primary relationships to COVID-19 (based on the 'Disposition' page)

#### **Protocol deviations**

The number (%) of participants in the FAS with any confirmed protocol deviation will be tabulated by deviation category (as specified in the study Data Handling Plan). All protocol deviations will be listed. For all important protocol deviations, the relationship to COVID-19 will also be captured.

#### 2.3.2 Demographics and other baseline characteristics

The FAS and EFF will be used for all baseline and demographic summaries unless otherwise specified. Listings will be provided using the FAS.

#### Basic demographic and background data

All demographic and baseline disease characteristics data will be summarized and listed. Categorical data (e.g. Age groups: < 65 and  $\ge 65$  years, race, ethnicity, ECOG performance

status, others as applicable) will be summarized by frequency counts and percentages; the number and percentage of participants with missing data will be provided. Continuous data (e.g. age, weight, height, body mass index, PSA level at screening from central laboratory for subgroup participants who had prior RP and participants who had prior curative intent RT, separately) will be summarized by descriptive statistics (N, mean, median, 1st and 3rd quartile, standard deviation, minimum and maximum).

#### Diagnosis and extent of cancer

Summary statistics will be tabulated for diagnosis and extent of cancer. This analysis will include the following for all participants: PSA level at time of initial cancer diagnosis (ng/mL), primary tumor clinical stage (i.e. T2c or less, T3, T3a, T3b, T4 and Tx), regional lymph node clinical stage, distant metastasis clinical stage, biopsy predominant histology/cytology, percentage of each histological type/pattern, biopsy Gleason score (i.e.  $\leq$  6, 7 (3+4), 7 (4+3), 8, and 9 or 10), initial definitive therapy received, time since initial diagnosis to first injection (in months), time from initial diagnosis to biochemical recurrence diagnosis (in months), the time since primary definitive therapy to diagnosis of BCR, time since biochemical recurrence diagnosis to the first injection (in days), PSA level at biochemical recurrence diagnosis (ng/mL). Note: biopsy Gleason score will be displayed along with the score details for each score combination in the listing.

For participants who underwent radical prostatectomy: primary tumor pathological stage, regional lymph node pathological stage, distant metastasis pathological stage, radical prostatectomy Gleason score (i.e.  $\leq$  6, 7 (3+4), 7 (4+3), 8, and 9 or 10), radical prostatectomy residual disease status. Note: Radical prostatectomy Gleason score will be displayed along with the score details for each score combination in the listing.

For participants who underwent curative intent radiation therapy: Nadir PSA level (ng/mL)

#### **Derivations:**

Time since initial diagnosis to the first injection (in months) = (date of the first injection – date of first prostate cancer diagnosis + 1) / 30.4375

Time from initial diagnosis to biochemical recurrence diagnosis (in months) = (biochemical recurrence diagnosis - date of first prostate cancer diagnosis + 1) / 30.4375

Time since biochemical recurrence to the first injection (in days) = date of the first injection – biochemical recurrence + 1

#### **ECOG Performance Status**

ECOG performance status at baseline will be presented in a summary table and will be listed.

#### **Medical history**

Medical history and ongoing conditions, including cancer-related conditions and symptoms entered on (e)CRF will be summarized and listed. Separate summaries will be presented for ongoing and historical medical conditions. The summaries will be presented by primary system

organ class (SOC), preferred term (PT). Medical history and current medical conditions will be coded using the Medical Dictionary for Regulatory Activities (MedDRA) terminology. The MedDRA version used for reporting will be specified in the CSR and as a footnote in the applicable tables/listings.

# 2.4 Treatments (study treatment, rescue medication, concomitant therapies, compliance)

#### 2.4.1 Study treatment / compliance

The following exposure information of [F]CTT1057 and [Ga]Ga-PSMA-11, as reported in the study treatment page of the eCRF, will be summarized for the F-SAF and Ga-SAF:

- Radioactivity dose administered (MBq)
- Number (%) of participants who were dosed but with extravasation during administration
- Number of participants with dose administered outside the planned range:
  - for [ $^{18}$ F]CTT1057 : < 266 MBq or > 407 MBq
  - for  $[^{68}$ Ga]Ga-PSMA-11 : < 111 MBq or > 185 MBq
- Time (in minutes) from injection to full-body PET imaging acquisition start time
- Number (%) of participants with additional pelvic PET imaging acquisition, with time from injection to additional pelvic PET imaging acquisition start time if applicable

An additional summary of the time (in days) between the [F]CTT1057 and [Ga]Ga-PSMA-11 PET scan dates will be provided using the SAF.

Participant level listings of doses administered or not, along with reasons if not administered will be produced using the FAS.

#### 2.4.2 Prior, concomitant and post therapies

#### **Prior anti-cancer therapy**

The number and percentage of participants who received any prior anti-neoplastic medications, prior anti-neoplastic radiotherapy or prior anti-neoplastic surgery will be summarized. Prior anti-neoplastic medications will be summarized by total number of regimens, setting (e.g. adjuvant, metastatic, etc.) and also by lowest ATC class and preferred term.

Prior anti-neoplastic radiotherapies will be summarized by method (i.e. external beam vs. internal beam) and setting.

Prior anti-neoplastic surgeries will be summarized by procedure (i.e. radical prostatectomy vs. other) and residual disease (e.g. yes, no, etc.)

Separate listings will be produced for prior anti-neoplastic medications (including regimen number, setting and intent), radiotherapy, and surgery. Anti-neoplastic medications will be coded using the WHO Drug Dictionary (WHO-DD); anti-neoplastic surgery will be coded using MedDRA. Details regarding MedDRA and WHO-DD version will be included in the footnote in the tables/listings.

The above summary tables will be performed using the FAS and EFF and listings will be provided using the FAS.

#### Concomitant medications

Concomitant therapy is defined as all interventions (therapeutic treatments and procedures) other than the study treatment administered to a participant coinciding with the study treatment Concomitant therapy medications period. includes drugs)/therapies/procedures starting on or after the start date of study treatment or medications/therapies/procedures starting prior to the start date of study treatment and continuing after the start date of study treatment.

Concomitant medications will be coded using the World Health Organization (WHO) Drug Reference Listing (DRL) dictionary that employs the WHO Anatomical Therapeutic Chemical (ATC) classification system and summarized by lowest ATC class and preferred term using frequency counts and percentages. Surgical and medical procedures will be coded using MedDRA and summarized by SOC and preferred term. These summaries will include:

- 1. Medications/therapies/procedures starting within 14 days of [18F]CTT1057 (or [68Ga]Ga-PSMA-11) as long as they are prior to [68Ga]Ga-PSMA-11 (or [18F]CTT1057) dose (if applicable)
- 2. Medications/therapies/procedures starting prior to start of study treatment and continuing after the start of study treatment.

Number of participants (%) who received diuretics (e.g. Furosemide) as concomitant medication on the day of PET/CT scans will also be summarized.

All concomitant therapies will be listed. Any concomitant therapies starting and ending prior to the start of first dose of study treatment or starting more than 14 days after the last date of study treatment will be flagged in the listing. Concomitant medication summary tables will be provided using the F-SAF and Ga-SAF separately, and listings will be provided for the SAF.

#### 2.5 Analysis supporting primary objective(s)

The primary objectives of the study are to evaluate the region-level CLR of [18F]CTT1057, and to evaluate the patient-level PPV (with anatomical localization) of [18F]CTT1057.

#### 2.5.1 **Primary endpoint(s)**

The co-primary endpoints evaluated for participants in the EFF are the following:

Region-level CLR: Proportion of regions containing at least one TP lesion (anatomically localized correspondence between PET imaging and the reference standard), regardless of any co-existent FP findings within the same region, out of all regions containing at least one PETpositive finding by central assessments. See Section 1.2.1 for Primary Estimand.

Patient-level PPV: Proportion of participants who have at least one TP lesion (anatomically localized correspondence between PET imaging and the reference standard), regardless of any co-existent FP findings, out of all participants who are PET/CT scan positive by central assessments. See Section 1.2.1 for Primary Estimand.

Centralized imaging assessments (CTS Level 2) will be used as reference standard if pathology assessment (CTS Level 1) is not available for a lesion, inconclusive or negative (for biopsy only).

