### 1.1 Study design

This is a prospective, open-label, multi center, single-arm Phase III study to evaluate the diagnostic performance of [F]CTT1057 as a PET imaging agent for detection and localization of PSMA positive tumors in prostate cancer patients diagnosed with biochemical recurrence (BCR) after initial definitive therapy with either radical prostatectomy (RP) or curative intent radiation therapy (RT), using a composite truth standard (CTS) as reference.

Approximately 190 participants will be enrolled to ensure at least 152 participants are evaluable for the co-primary endpoints. [F]CTT1057 PET/CT scan imaging will be centrally read by 3 independent nuclear medicine physicians who will be blinded to any other participant data. See study protocol Section 4.1 and Section 8.3.1 for central read details.

The CTS to be used as reference will be hierarchical in nature, with 3 levels of Standard of Truth (SoT) procedures, that will be applied as follows:

#### Level 1

• **Histopathology** if available for a lesion (from prospective biopsy or salvage surgery performed within 8 weeks after the [F]CTT1057 PET/CT scan); OR in case that histopathology is not available for a lesion, inconclusive (i.e. if biopsy/surgery tissue sample is not evaluable for histopathology assessment due to sample quality or inadequate quantity or any other technical causes) or negative (for biopsy only):

#### Level 2

• Imaging diagnostic procedures performed on each participant as clinically indicated per SoC, which must include the [68Ga]Ga-PSMA-11 PET/CT scan that is mandatory for all participants randomized in the study and at least high resolution CT scan (covering at least chest, abdomen, and pelvis and any other region as clinically indicated) with intravenous and oral contrast (or MRI if CT scan with contrast is medically contraindicated). The high resolution CT scan and any other imaging diagnostic procedure clinically indicated as per SoC must be acquired within the 8 weeks either prior to or following the [18F]CTT1057 PET/CT scan. Three-month follow-up imaging (from baseline) will also be used as part of the CTS Level 2 in cases where it is clinically required for the diagnosis of particular lesion(s); OR if neither of the two above are feasible or deemed appropriate or they are inconclusive (i.e. images are not interpretable due to poor or inadequate image quality that precludes reliable assessment):

#### Level 3

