• 50% or greater decline in PSA following radiation therapy (as long as no concomitant androgen deprivation therapy (ADT) is given) as per PCWG3 criteria (Scher et al 2016).

[figure not shown]
In the cases where pathology will be available (CTS Level 1), assessments by the local pathologists will be performed as per SoC, and results should be available within 2 weeks after surgery. Pathologists will be blinded to the [18F]CTT1057 PET/CT data. In this case, only pathology will be used as SoT for the concerned lesion(s).

In the cases where pathology will not be available for a lesion, the central read results of the [68Ga]Ga-PSMA-11 PET/CT scan (performed for all participants randomized) and other imaging diagnostic procedures to be performed on each participant for the CTS Level 2 will be used as SoT for the co-primary endpoint calculations. See study protocol Section 4.1 for central read details.

All participants will undergo a [Ga]Ga-PSMA-11 PET/CT as part of the study, for both the CTS Level 2 (in case it is required as SoT) and the secondary endpoint of assessment of concordance between [F]CTT1057 and [Ga]Ga-PSMA-11 for detection of lesions (as detailed in the study protocol Section 2).

In addition to central review, local review of SoC images (including [Ga]Ga-PSMA-11) will be performed to be used by the treating physician/Clinical Study Investigator for participant management decisions and overall assessment. See study protocol Section 8.3.1 for assessment details and Section 6.4 for blinding requirements.

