## 2.5.2 Statistical hypothesis, model, and method of analysis

For region-level CLR, the observations (regions positive/negative status) are clustered within a participant. Observations within participants (clusters) are correlated, which may lead to biased estimates of region-level CLR when the correlated nature of the data within each cluster is ignored. More important, an analysis ignoring correlation often yields a misleading small estimated standard error (and 95% CI) for CLR because it erroneously counts all observations as independent observations. Region-level CLR adjusted for correlation among observations within participants can be modeled by using a logistic regression model with random effects (Gatsonis CA 1995, Verbeke G, Molenberghs G 2000).

When calculating CLR, the number of TP regions  $(y_i)$ , follows the binomial distribution with parameter  $(n_i, p_i)$ ,

$$y_i|b_i\sim \text{Binomial}(n_i,p_i)$$

 $p_i$  denotes the probability of TP among all positive PET regions (TP or FP) for participant i, and  $n_i$  corresponds to the denominator in the CLR definition, i.e. the number of all regions containing at least one PET-positive finding by central assessments (TP or FP regions) for participant i.

The number of TP and FP regions overall (i.e. across all five regions, which are prostate region, PLN, skeletal, extra-pelvic lymph nodes and visceral) and by region across all participants in the EFF will be presented, along with region-level CLR and two-sided 95% CIs estimated using the following logistic regression model with random effects.

$$\log\left(\frac{p_i}{1-p_i}\right) = \mu + b_i$$

where  $p_i$  is the region-level CLR for participant i,  $\mu$  is the fixed effect of overall mean,  $b_i$  is the random effect for participants (clusters).  $b_i$  follows a normal distribution:  $b_i \sim N(0, \sigma_h^2)$ .

The lower bound of the 95% CI should be greater than 0.50 to attain the first co-primary endpoint.

**For patient-level PPV**, the number of TP and FP participants, as well as the number of positive and negative (and inconclusive, if applicable) [F]CTT1057 PET/CT scans, will be presented, along with patient-level PPV with two-sided exact binomial 95% CIs (Clopper and Pearson 1934).

The lower bound of the 95% CI for patient-level PPV should be greater than 0.20 attain the second co-primary endpoint.

The same analysis for patient-level PPV will be repeated by CTS Level.

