#### 2.5.5 Sensitivity analyses

For participants where CTS Level 1 or 2 is used as the truth standard for the primary analysis, the next lower level of CTS will be used to verify positivity or negativity for the sensitivity analysis, if available. For instance, if pathology (CTS Level 1) is used for a lesion as the truth standard for the primary estimand, the imaging component of CTS (Level 2) will be used as truth standard for sensitivity analysis for the primary estimand. Similarly, results of CTS Level 2 will be replaced by CTS Level 3 if applicable. However, for those using changes in PSA level (CTS Level 3) as the truth standard for primary estimand, their positivity status cannot be replaced by another component of CTS for sensitivity analysis.

Region-level CLR along with its 95% CI will also be computed based on the weighted estimator approach (Lee and Dubin 1994) for each central reader as following:

$$\hat{p}_w \pm 1.96 \hat{\sigma}/\sqrt{n}$$
.

 $\hat{p}_w$  is the point estimator with  $\hat{p}_w = \sum_{i=1}^n \hat{p}_i / n$  and  $\hat{p}_i = y_i / n_i$ , where  $y_i$  and  $n_i$  are the same as defined in Section 2.5.2 above and n represents the number of participants with at least one PET-positive finding by central assessments.  $\hat{\sigma}$  is the estimated standard deviation of  $\hat{p}_i$ .

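### Evaluable negative biopsies are replaced by imaging while positive ones stand, so the Level 1 PPV row is inflated and no planned analysis keeps a negative biopsy as a false positive

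*SAP*

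**What the plan says.** SAP 2.5.1 replaces Level 1 pathology by centrally read imaging when pathology "is not available for a lesion, inconclusive or negative (for biopsy only"). Protocol Sections 3, 4.1, 8.3.1 and 12.4.1 carry the same rule.

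SAP 1.1 treats technical failure as a separate category: "inconclusive (i.e. if biopsy/surgery tissue sample is not evaluable for histopathology assessment due to sample quality or inadequate quantity or any other technical causes"). Negative, for a biopsy, therefore means an evaluable sample without cancer. Level 1 tissue comes "from prospective biopsy or salvage surgery", and the override is limited to biopsy, so negative surgical histology stays at Level 1.

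SAP 1.1 (and Protocol Section 3) also says of lesions with pathology: "In this case, only pathology will be used as SoT for the concerned lesion(s").

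Two planned analyses depend on the level that decides a lesion. SAP 2.5.2: "The same analysis for patient-level PPV will be repeated by CTS Level". SAP 2.5.5: "the next lower level of CTS will be used to verify positivity or negativity for the sensitivity analysis, if available", followed by "Similarly, results of CTS Level 2 will be replaced by CTS Level 3 if applicable".

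**The concern.** The rule works in one direction. A positive biopsy is final. A negative one is re-judged by imaging that must include [68Ga]Ga-PSMA-11, a tracer for the same target as the test agent. A PET-positive lesion with a negative biopsy would be a false positive on histology; after the override it is either still a false positive or a true positive. The count of PET-positive regions or participants does not change, so the observed CLR and PPV can only stay the same or rise.

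Two things are at stake. A reader of the by-level table will take the Level 1 row as histologic validation, yet the biopsies that would count against the tracer have left that row. And the report will contain no figure showing how far the co-primary results depend on the override. SAP 1.1 adds a practical risk: its only-pathology sentence and the override in SAP 2.5.1 give different labels for the same biopsied lesion, and those labels feed both co-primaries.

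**Working it through.** **1. The plan's own PPV figure.** Inputs from SAP 3.1: null 0.20, alternative 0.33, one-sided 2.5%, 80% PET-positive, 20% dropout. By the exact binomial, the smallest n with at least 90% power is 122 PET-positive participants (success at 34 or more of 122; alpha 0.0228, power 0.905, Clopper-Pearson lower bound 0.2013). Then 122/0.8 = 152.5, stated as 152, and 152/0.8 = 190. The design reproduces, and 122 is the base for turning percentage points into participants.

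**2. Where each PET-positive lesion goes** (SAP 1.1, 2.5.1, 2.5.5).

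| Pathology result | Primary truth | Possible label | Step-down analysis |
|---|---|---|---|
| Biopsy positive | Level 1 | TP | Level 2 |
| Biopsy negative, evaluable | Level 2 | TP or FP | Level 3 if applicable, else Level 2 |
| Biopsy not evaluable | Level 2 | TP or FP | Level 3 if applicable, else Level 2 |
| Surgery positive | Level 1 | TP | Level 2 |
| Surgery negative | Level 1 | FP | Level 2 |

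No path restores a negative biopsy. The weighted CLR estimator in SAP 2.5.5 and the subgroups and covariate models in SAP 2.5.6 keep the same truth labels.

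**3. The Level 1 row.** Let q be the share of PET-positive cases with evaluable pathology that are positive, and s the surgical share of pathology. Neither is in the documents. Take one assessed lesion per case and the same q for biopsy and surgery. Negative biopsies leave the row, so

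Level 1 PPV as planned = q / (q + s(1 - q)); with all evaluable results counted it is q.

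For q = 0.70:
- s = 0: 0.70/0.70 = 1.00
- s = 0.10: 0.70/0.73 = 0.96
- s = 0.25: 0.70/0.775 = 0.90
- s = 0.50: 0.70/0.85 = 0.82
- s = 1: 0.70/1.00 = 0.70, no inflation

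For q = 0.90 the gap is smaller: 0.99 at s = 0.10 and 0.95 at s = 0.50, against 0.90.

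**4. The overall PPV.** Upper bound on the shift = f x (1 - q) x r, where f is the share of PET-positive participants with pathology and r the share of negative biopsies called positive at Level 2. Protocol 4.1 gives 35-40% availability among patients; applying it to PET-positive participants is an assumption. Negative biopsies at 10-30% and r at 0.5-1.0 are also assumptions.
- Low: 0.35 x 0.10 x 0.5 = 0.0175, or 1.8 points (0.0175 x 122 = 2.1 participants)
- High: 0.40 x 0.30 x 1.0 = 0.12, or 12 points (0.12 x 122 = 14.6 participants)

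Both treat all pathology as biopsy and assume that no affected participant has another true-positive lesion, so each is a ceiling for its inputs. With r = 0 the shift is nil. No CLR size is given because the documents have no region-level pathology share; only its direction is established.

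**The case against.** The rule is deliberate, prespecified and stated repeatedly in both documents. A needle can miss a small lesion, so treating every negative biopsy as proof of a false positive would penalise the tracer for sampling error. That stands, and it is a reason to keep the primary rule. It is not a reason to omit an analysis of what the rule does.

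Several stronger readings are tempting and are not supported:
- *PPV in biopsied participants is 100% by construction.* Overridden lesions go to Level 2, where they can still be false positives. The Level 1 row also holds negative surgical histology. A participant can be a false positive because nothing is correctly localized (SAP 2.6.1). Only the lesion-level statement holds: a Level 1 verdict from biopsy cannot be a false positive on histology.
- *Level 1 is the only row free of PSMA imaging.* Level 3 rests on PSA response after radiotherapy and has its own row.
- *Overridden biopsies always stay on imaging in the sensitivity analysis.* They may move to Level 3 where it applies, and can become false positives there. The biopsy result itself is still not used.
- *PPV will be about 12 points too high.* PPV needs only one true-positive lesion per participant, and Protocol 4.1 says pathology covers only a subset of lesions, so many overrides will change nothing at participant level.

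On the only-pathology sentence, the endpoint sections consistently state the override, so misprogramming is unlikely. The wording still conflicts.

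**Conclusion.** The concern holds in limited form. An evaluable negative biopsy leaves Level 1 while a positive one stays, so the planned Level 1 PPV overstates histologic confirmation whenever negative biopsies occur. At an assumed 70% positive pathology it reads about 100% with no surgical cases and 82-96% with 50-10% surgical cases, against 70%. The observed CLR and PPV can only be unchanged or raised, and no planned sensitivity or supplementary analysis keeps a negative biopsy as a false positive. The 1.8 to 12 point shift in overall PPV is an upper bound on the assumptions in the working, not an expected effect. The co-primary hypotheses are framed against the composite standard, so this does not show that the primary test is invalid. It shows that its dependence on the override will go unreported.

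**What to change.** Keep the primary rule and make three changes.

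1. SAP 2.5.5: add one sensitivity analysis of both co-primaries, per reader, in which an evaluable negative biopsy stays as the truth and the lesion is a false positive. The participant or region remains a true positive if another of its lesions is one. Label the result a lower bound, because some negatives are sampling misses.
2. SAP 2.5.2: report how many biopsies were overridden and their Level 2 result. Split Level 1 into biopsy and surgery. Add a separate histology-only PPV whose denominator is every PET-positive lesion or participant with an evaluable biopsy or surgical result. Show it beside the by-level rows, so that those still reconcile with the primary result. State how a participant with lesions decided at different levels is assigned, since SAP 2.5.2 gives no rule.
3. SAP 1.1 and Protocol Section 3: reconcile the only-pathology sentence with the override in SAP 2.5.1.

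The cost is SAP wording and one extra run. Protocol 8.3.2 already records pathology outcome and location in the eCRF, so no new data, reads or participants are needed. The supporting figures will be somewhat less favourable.
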